15.2.3. Severity of Events

The following definitions should be considered when evaluating the severity of AEs and SAEs:

Severity of Event	
Mild	The event is easily tolerated by the subject and does not affect the subject's usual daily activities.
Moderate	The event causes the subject more discomfort and interrupts the subject's usual daily activities.
Severe	The event is incapacitating and causes considerable interference with the subject's usual daily activities.

15.2.4. Expectedness of Events

Expectedness of all AEs will be determined by the Sponsor (or designee) according to the Investigator's Brochure.

15.3. Monitoring and Recording Events

15.3.1. Adverse Events

For subjects who receive study treatment, any AE experienced between the time of signing the ICF and Part 2 Final Follow-up Evaluation/Telephone Call (or End of Part 1 Evaluation, if the subject does not enroll in Part 2) will be recorded on the CRF, regardless of the severity of the event or its relationship to study treatment injection or sham procedure in Part 1. For subjects who never receive study treatment, no AEs need to be recorded on the applicable CRF.

15.3.2. Serious Adverse Events

For subjects who receive study treatment, any SAE experienced between the time of signing the ICF and Part 2 Final Follow-up Evaluation/Telephone Call (or End of Part 1 Evaluation, if the subject does not enroll in Part 2) will be recorded on an SAE form and on the applicable CRF,

CONFIDENTIAL

The information contained herein may not be used, disclosed, or published without the written consent of Biogen MA Inc.

regardless of the severity of the event or its relationship to study treatment. For subjects who never receive study treatment, any SAE occurring between the time of signing the ICF and Part 2 Final Follow-up Evaluation/Telephone Call (or End of Part 1 Evaluation, if the subject does not enroll in Part 2) must be recorded on an SAE form, regardless of the severity of the event or its relationship to study treatment; however, the SAE does not need to be recorded on the applicable CRF.

SAEs must be reported to the safety vendor listed in the Study Reference Guide within 24 hours as described in Section 15.3.3. Follow-up information regarding an SAE also must be reported within 24 hours.

Subjects will be followed for all SAEs until their Part 2 Final Follow-up Evaluation/Telephone Call (or End of Part 1 Evaluation, if the subject does not enroll in Part 2). Thereafter, the event should be reported as described in the Study Reference Guide only if the Investigator considers the SAE to be related to study treatment.

Any SAE that is ongoing when the subject completes or discontinues the study will be followed by the Investigator until the event has resolved, stabilized, or returned to baseline status.

15.3.3. Immediate Reporting of Serious Adverse Events

In order to adhere to all applicable laws and regulations for reporting an SAE, the study site must formally notify the safety contact as described in the Study Reference Guide within 24 hours of the study site staff becoming aware of the SAE. It is the Investigator's responsibility to ensure that the SAE reporting information and procedures are used and followed appropriately.

Reporting Information for SAEs

Any SAE that occurs between the time that the subject's parent or legal guardian has signed the ICF and Part 2 Final Follow-up Evaluation/Telephone Call (or End of Part 1 Evaluation, if the subject does not enroll in Part 2) must be reported as described in the Study Reference Guide, within 24 hours of the study site staff becoming aware of the event. Thereafter, the event should be reported only if the Investigator considers it related to study treatment.

A report ***must be submitted*** as described in the Study Reference Guide regardless of the following:

- Whether or not the subject has undergone study-related procedures
- Whether or not the subject has received study treatment
- The severity of the event
- The relationship of the event to study treatment

To report initial or follow-up information on an SAE, fax or email a completed SAE form as described in the Study Reference Guide.

CONFIDENTIAL

The information contained herein may not be used, disclosed, or published without the written consent of Biogen MA Inc.

15.3.3.1. Deaths

Death is an outcome of an event. The event that resulted in death should be recorded on the appropriate CRF. All causes of death must be reported as SAEs within 24 hours of the site becoming aware of the event. The Investigator should make every effort to obtain and send death certificates and autopsy reports as described in the Study Reference Guide. The term death should be reported as an SAE only if the cause of death is not known and cannot be determined.

15.3.4. Suspected Unexpected Serious Adverse Reactions

SUSARs are SAEs that are unexpected and judged by the Investigator or the Sponsor (or designee) to be related to the study treatment administered.

The Sponsor (or designee) will report SUSARs to the appropriate regulatory authorities and to Investigators as required, according to local law.

15.4. Procedures for Handling Special Situations

15.4.1. Dosing Errors

All dosing errors (including, but not limited to, route of administration and wrong dose) must be reported as protocol deviations. A brief description should be provided in the deviation report, including information about whether the subject was symptomatic or not. Dosing details should be captured on the Dosing CRF.

A dosing error will be considered an overdose when any of the following conditions are met:

- Any single dose given exceeds the dose level described in the protocol and DHA Guidelines.
- Dosing frequency exceeds 4 doses in a 60-day period.
- Study drug is administered less than 14 days from the previous dose.

Overdoses are not considered AEs and should not be recorded as an AE on the CRF unless an AE or an SAE occurs. All overdoses (regardless of whether or not they result in an AE) must be recorded on an overdose form and faxed to Biogen or designee within 24 hours of the site becoming aware of the overdose. If an overdose results in an SAE, both the SAE and overdose forms must be completed and faxed to Biogen or designee. Should an overdose occur, the Investigator or designee must contact the Medical Monitor within 24 hours; refer to the Study Reference Guide for complete contact information.

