7.2.2. Treatment

Part 1

Eligible subjects will be admitted to the study site on Part 1 Day 1, undergo predose evaluations, and then receive an LP injection of Nusinersen or a sham procedure. After the injection on Day 1, subjects will remain at the study site for at least 24 hours after the procedure for safety monitoring.

Subjects will return to the study site on Days 15, 29, 64, 183, and 302 (± 1 day for Days 15 and 29 and ± 7 days for all other days) for follow-up evaluations and subsequent injections of study treatment or sham procedure, for a total of 6 injections or sham procedures over a dosing period of 10 months. During these 5 evaluations, all subjects will remain at the study site for at least 6 hours postdose for safety monitoring. An overnight stay is optional, at the discretion of the Investigator. Safety monitoring by telephone contact will occur on the day after injection of study treatment or sham procedure. In addition, the study site will monitor the subject's condition through telephone contact every other week (excluding weeks with study visit) throughout the study period.

After completing the End of Part 1 Evaluation assessments, all eligible subjects may elect to enroll in Part 2.

Based on emergent data from the Nusinersen clinical development program, the Sponsor may decide to terminate Part 1 early, and all subjects may be offered the opportunity to transition to Part 2 prior to completion of all Part 1 Evaluation assessments. All subjects enrolled in the study at the time of Sponsor termination will be considered Part 1 completers. The next study evaluation for those subjects will serve as an End of Part 1 Evaluation, which may occur at any time prior to the next scheduled Part 1 study evaluation.

Unblinding will occur in order for the subjects to transition from Part 1 to Part 2.

End of Part 1 Evaluation assessments are required to be done prior to the transition to Part 2. After performing the End of Part 1 Evaluation assessments, the subject may immediately transition to Part 2.

Part 2

Part 2 study procedures and schedules will be determined based on the subject's treatment assignment in Part 1.

CONFIDENTIAL

The information contained herein may not be used, disclosed, or published without the written consent of Biogen MA Inc.

Subjects who were randomized to receive Nusinersen in Part 1

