12. STUDY TREATMENT MANAGEMENT

Study site staff should follow the DHA for specific instructions on the handling, preparation, administration, and disposal of the study treatment. The DHA supersedes all other references (e.g., protocol).

Study treatment must be dispensed only by a pharmacist or medically qualified staff. Study treatment is to be dispensed only for subjects enrolled in this study. Once study treatment is prepared for a subject, it can be administered only to that subject. Study treatment vials are for one-time use only; any study treatment remaining in the vial should not be used for another subject.

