15.4. Procedures for Handling Special Situations

15.4.1. Overdose

An overdose is any dose of study treatment given to a subject or taken by a subject that exceeds the dose described in the protocol; an overdose must be documented as a protocol deviation. A brief description should be provided in the deviation form, including whether the subject was symptomatic (with a list of symptoms) or asymptomatic. Overdoses are not considered AEs and should not be recorded as an AE on the CRF; however, all overdoses must be reported to the Medical Monitor within 24 hours of the site becoming aware of the overdose. An overdose must be reported to the Medical Monitor even if the overdose does not result in an AE. If an overdose results in an AE, then the AE must be recorded. If an overdose results in an SAE, then the SAE form must be completed and faxed as described in the Study Reference Guide. All study treatment-related dosing information must be recorded on the dosing CRF.

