### **3.5 Protocol deviations**

Protocol deviations identified during site monitoring will be captured in a protocol deviation log and categorized as major or minor deviations. These deviations will be listed. Major protocol deviations will be summarized for only Part 2 as part of this SAP.

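### Does an in-window loading dose on Day 15 or Day 29 count as an overdose under the 14-day interval rule?

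*Protocol*

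**What the plan says.** Section 15.4.1 of protocol version 4 requires every dosing error to be reported as a deviation and gives wrong route and wrong dose as open-ended examples. It then says: "A dosing error will be considered an overdose when any of the following conditions are met". Three conditions follow: a single dose above the stated level; "Dosing frequency exceeds 4 doses in a 60-day period"; and "Study drug is administered less than 14 days from the previous dose". Every overdose "must be recorded on an overdose form and faxed to Biogen or designee within 24 hours", and the Medical Monitor must be contacted within the same time. An overdose is not recorded as an adverse event unless one occurs.

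Section 7.2.2 sets the loading doses on Days 1, 15, 29 and 64, with a tolerance of plus or minus "1 day for Days 15 and 29" and 7 days on later visits. It does so for Part 1 and again for former sham subjects in Part 2. Tables 2 and 4 show the same windows.

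Versions 1 to 3 have no interval condition. There an overdose is a dose "that exceeds the dose described in the protocol; an overdose must be documented as a protocol deviation".

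SAP Section 3.5 lists the deviations found at site monitoring, graded major or minor, and adds: "Major protocol deviations will be summarized for only Part 2 as part of this SAP".

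**The concern.** The interval threshold equals the nominal interval and carries no tolerance. A dose given one day early, or on time after a dose given one day late, therefore falls below it while staying inside the visit window. Section 15.4.1 neither exempts in-window doses nor says whether they can be dosing errors.

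Two sites could then handle the same dose differently. One would report nothing. The other would file a deviation, send an overdose form and call the Medical Monitor, all for a dose that followed the schedule. In a study whose primary objective is safety, uneven overdose reporting is worth checking, and the difference would carry into the deviation listing under SAP Section 3.5.

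**Working it through.** **Inputs.** Dose 1 on Day 1; dose 2 on Day 14, 15 or 16; dose 3 on Day 28, 29 or 30; dose 4 on Days 57 to 71 (Section 7.2.2). Threshold: a gap below 14 days (Section 15.4.1). The gap is the later day minus the earlier day.

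**Nominal schedule first.** 15 − 1 = 14 and 29 − 15 = 14. Neither is below 14, so dosing on the exact nominal days never meets the condition.

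**All permitted pairs.**

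| Dose 2 | Dose 3 | First gap | Second gap | Any gap below 14? |
|---|---|---|---|---|
| 14 | 28 | 13 | 14 | yes |
| 14 | 29 | 13 | 15 | yes |
| 14 | 30 | 13 | 16 | yes |
| 15 | 28 | 14 | 13 | yes |
| 15 | 29 | 14 | 14 | no |
| 15 | 30 | 14 | 15 | no |
| 16 | 28 | 15 | 12 | yes |
| 16 | 29 | 15 | 13 | yes |
| 16 | 30 | 15 | 14 | no |

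Six of 9 pairs meet the numerical condition. If both dosing days are counted (one day added to each gap), only the pair 16 and 28 does, at 13 days, so 1 of 9. The protocol does not say how days are counted. These are counts of calendar combinations and not expected frequencies.

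**Other conditions.** Dose 3 to dose 4 is 57 − 30 = 27 to 71 − 28 = 43 days, never below 14. Four doses can fall in 60 days (Day 1 to Day 57), but the fifth is no earlier than 183 − 7 = Day 176, so more than 4 in 60 days cannot occur in-window. Only the interval condition touches the windows.

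**How many doses.** The condition concerns study drug, so sham procedures do not count. The planned maximum is 14 × 2 = 28 intervals in Part 1 and 7 × 2 = 14 for former sham subjects in Part 2, 42 in all.

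The rule exists only in version 4. Version 4 describes CS3B as finished (Section 5.3.2) and reports US approval in December 2016 and later European approval (Section 5.2). Version 3 lists CS3B as ongoing. SAP Section 1.3 says that Part 1 ended after an interim analysis of CS3B. Version 4 therefore appears to follow the decision to stop Part 1, which removes most or all of the 28. Of the other 14, SAP Section 1.2 already writes of the loading doses in the past tense, and Part 2 with its loading schedule was already in versions 2 and 3.

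**What the label feeds.** SAP Section 5.1.6 has no overdose table. SAP Section 3.3 counts doses and amounts whatever they are called. In SAP Section 4.1, Days 14 to 16 all fall in the Day 15 window (above 1 to 22) and Days 28 to 30 in the Day 29 window (above 22 to 47). Only the deviation listing, and the Part 2 summary if such a dose were graded major, could differ.

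**The case for a change.** The best case for acting is textual. The dose-level condition refers back to the protocol and the Directions for Handling and Administration (DHA), whereas the interval condition is a bare number with no mention of the schedule. Dosing errors are defined only by examples, and timing is not among them. Section 11.2 does not help, since it covers schedule changes for concurrent illness. The pair 16 and 29 is awkward: a third dose on its exact nominal day meets the condition. The rule also triggers 24-hour reporting, and one sentence would clear it up.

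Most of this stands as a description of the wording: the text does not state that an in-window dose is exempt. What does not follow is that the sections contradict each other. The conditions apply to dosing errors, and to reach an in-window dose a reader must pass over those opening words. Nor is it shown that sites differed. Deviations are identified at monitoring and graded, a step that can even out differences in self-reporting, and the DHA, which Section 12 says overrides the protocol on administration, may settle the point. It is not available here.

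The low cost of a sentence is a fair argument, but it would probably govern no future dose: Part 2 takes only Part 1 participants, and the SAP says all subjects leave early for study CS11.

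**Conclusion.** No change to the plan. Permitted gaps of 12 or 13 days do exist, in 6 of 9 date pairs. Read with its opening words, however, the overdose rule need not reach a dose given within the window. The remaining gap is an unwritten definition that those grading deviations can fill sensibly by treating early in-window loading doses in one consistent way. No endpoint, table of adverse events or conclusion moves.

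The exposure is at most 42 intervals on paper, more realistically at most 14, and possibly none. That narrowing rests on inference from the documents' own chronology. The effective date of version 4 and the dates of the loading doses are not given, so zero is not proven. If the sponsor wishes to reconcile the wording of Sections 7.2.2 and 15.4.1, which of them governs is for the clinical team. The analysis does not depend on the answer.

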15.4.2. Medical Emergency

In a medical emergency requiring immediate attention, study site staff will apply appropriate medical intervention, according to current standards of care. The Investigator or designee should contact [REDACTED], MD, Office: [REDACTED], Mobile: [REDACTED], Fax: [REDACTED] (or [REDACTED] medical emergency: [REDACTED] or [REDACTED]) or [REDACTED], MD at [REDACTED].

CONFIDENTIAL

The information contained herein may not be used, disclosed, or published without the written consent of Biogen MA Inc.

15.4.2.1. Unblinding for Medical Emergency

For Part 1 of this study, in a medical emergency when knowledge of the subject's treatment assignment may influence the subject's clinical care, the Investigator (or designee) should attempt to contact the blinded Biogen MA Inc. Medical Director or blinded [REDACTED] Medical Monitor to discuss the emergency within 24 hours. In these instances, the Investigator (or designee) may access the subject's treatment assignment by IRT.

The Investigator must document the reasons for unblinding in the subject's source documents. The Investigator is strongly advised not to divulge the subject's treatment assignment to any individual not directly involved in managing the medical emergency or to personnel involved with the analysis and conduct of the study.

15.5. Safety Responsibilities

15.5.1. The Investigator

The Investigator's responsibilities include the following:

- Monitor and record all AEs, including SAEs, regardless of the severity or relationship to study treatment.
- Determine the seriousness, relationship, and severity of each event.
- Determine the onset and resolution dates of each event.
- Complete an SAE form for each serious event and fax it as described in the Study Reference Guide within 24 hours of the study site staff becoming aware of the event.
- Pursue SAE follow-up information actively and persistently. Follow-up information must be reported as described in the Study Reference Guide within 24 hours of the study site staff becoming aware of new information.
- Ensure all AE and SAE reports are supported by documentation in the subjects' medical records.
- Pursue AE follow-up information, if possible, until the event has resolved or become stable.
- Report SAEs to local ethics committees, as required by local law.

15.5.2. The Sponsor

The Sponsor's responsibilities include the following:

- Before study site activation and subject enrollment, the Clinical Monitor (or designee) is responsible for reviewing with study site staff the definitions of AE and SAE, as well as the instructions for monitoring, recording, and reporting AEs and SAEs.
- The Sponsor (or designee) is to notify all appropriate regulatory authorities, central ethics committees, and Investigators of SAEs, as required by local law, within required time frames.

CONFIDENTIAL

The information contained herein may not be used, disclosed, or published without the written consent of Biogen MA Inc.

16. STATISTICAL METHODS AND DETERMINATION OF SAMPLE SIZE

Part 1 and Part 2 will be analyzed separately. For Part 1, in general, continuous variables will be summarized by descriptive statistics, including number, mean, median, standard deviation, minimum, and maximum. Categorical variables will be presented with the number and percentage in each category. For Part 2, no formal statistical analyses will be performed. Descriptive statistics will be presented for safety and efficacy data collected.

For the Part 1 analysis, baseline is defined as the last nonmissing assessment prior to the first dose of study treatment in Part 1. For the Part 2 analysis, baseline is defined as the last nonmissing assessment prior to the first dose of study treatment in Part 2. In addition, a pooled analysis incorporating data from both Part 1 and Part 2 will be conducted to characterize the safety profile of Nusinersen. For subjects on active treatment in Part 1, safety data from both Part 1 and Part 2 will be included in the pooled analysis and the Part 1 baseline will be used for those subjects in the pooled analysis. For subjects on sham procedure in Part 1, only safety data from Part 2 will be included in the pooled analysis and the Part 2 baseline will be used for those subjects in the pooled analysis.

Concomitant medication usage for each subject will be listed for review.

The objectives of the study and the endpoints to be analyzed are listed in Section 6.

16.1. Demographic and Baseline Characteristics

Demographic and baseline characteristics will be summarized using descriptive statistics by treatment group. Subject disposition will be summarized by treatment group. All subjects enrolled will be included in a summary of subject disposition.

16.2. Safety and Tolerability

Safety is the primary objective for the study. All AEs, laboratory abnormalities, ECGs, and vital signs will be evaluated for safety.

16.2.1. Analysis Population

Safety analyses will be conducted in the safety population. This safety set will include all subjects who are randomized and receive at least 1 dose of study treatment or sham procedure in Part 1. Treatment duration and amount of study treatment received will be summarized by treatment group.

16.2.2. Methods of Analysis

16.2.2.1. Neurological Examinations

Neurological examination findings will be listed for review, and as appropriate, results will be summarized descriptively for each treatment group. The number and percentage of subjects with shifts from baseline normal to each of the categorical values denoting normal, abnormal, and abnormal (not AE) will be summarized.

CONFIDENTIAL

The information contained herein may not be used, disclosed, or published without the written consent of Biogen MA Inc.

Note: If sedation was used, please allow sufficient recovery time for the subject to be fully engaged in the examination because change from baseline in neurological examinations outcome is a primary study endpoint. It is important that the data collected truly reflect the subject's neurological performance.

16.2.2.2. Adverse Events

All AEs will be analyzed based on the principle of treatment emergence. An AE will be regarded as treatment emergent if it was present prior to the first dose of study treatment and subsequently worsened, or was not present prior to the first dose of study treatment but subsequently appeared. The incidence of treatment-emergent AEs will be summarized overall, by severity, and by relationship to study treatment. A subject having the same AE more than once will be counted only once in the incidence for that event. The occurrence of the AE with the greatest severity will be used in the calculation of incidence by severity; the occurrence of the AE with the strongest relationship to study treatment will be used in the calculation of incidence by relationship to study treatment.

All treatment-emergent AEs and SAEs will be summarized for each treatment group using the Medical Dictionary for Regulatory Activities (MedDRA) coding system, by system organ class, preferred term, relationship to study treatment, and severity. Narratives of deaths, SAEs, early withdrawals from study treatment and from study due to AEs will be provided.

